2.7. Endpoints

The primary endpoint is the proportion of patients who are not able to complete treatment due to excessive toxicity. Toxicity will be tabulated by type, frequency, and severity of AEs and serious AEs (SAEs), laboratory abnormalities, and other safety findings.

The secondary endpoints are:

- Percentage of patients achieving a point in time objective response (either complete or partial response [CR or PR]) after 2 cycles of infigratinib. Tumor mapping will be performed from the endoscopic evaluation (after any biopsies) and this will be used to compare to pathologic (NUX/Ux cohort) or ureteroscopic (endoscopy cohort) findings in order to determine responses.
- Tumor mapping will be performed based on endoscopic findings, noting location, number of tumors, tumor architecture, and location of biopsies; and will again be performed during pathologic evaluation again noting size, location, number of tumors, architecture, and absence of tumor at any previously identified tumor. A difference of 3mm will be considered within error of measurement.
- Mutational analysis will be performed on FFPE tumor tissue using a comprehensive mutation panel (T200.2) which we have used in prior studies and includes all previously identified UTUC mutations, including all relevant FGFR3 alterations including hot spots, copy number variations and fusions. Blood collected at baseline will be used as germline source.
- All analyses will be performed on patients stratified as having or not having FGFR3 alterations. Descriptive statistics will be used to summarize various clinical parameters.
- The same methods will also be used to explore the association of AEs such as hyperphosphatemia with response.
- Percentage of patients with no evidence of disease 12 months after surgery

- Changes in patient reported QOL outcomes will be measured using a validated questionnaire (EORTC QLQ-C30 v3), administered at 3 time points: 1. enrollment (after enrollment and before first dose), 2. after completion of 2 cycles and prior to surgery, and 3. at 1 month postoperative check.

The exploratory endpoints are:

Tumor Studies:

- Single cell (sc)RNAseq will be performed on fresh frozen tumors using 10x Genomics platform. Tumor cell heterogeneity, FGFR3 gene expression, and tumor microenvironment will be profiled. All bioinformatics data analysis will be performed in the MD Anderson Genomics core as part of the Rare Tumor Initiative Program (2014-0938)

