5. TREATMENTS

5.1. Treatments Administered

Patients will receive infigratinib 125 mg orally every day for a total of 2 cycles. Each cycle will consist in 28 days, with a schedule of 3 weeks on, 1 week off. Surgery will be performed during weeks 8-9 (week 8 being the off-week of 2nd cycle), and patients will have taken last dose of Infigratinib at least 48 hours prior to surgery.

If patients are not able to tolerate the study drug, every effort will be made to schedule the surgery as soon as possible after the patient has recovered and/or the investigator determines it is the best course of action for the patient.

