8.2.7. Ophthalmic Assessments

Ophthalmologic examination will be performed by an ophthalmologist, or optometrist who is supervised by an ophthalmologist, at the times indicated in [Section 1](#). These assessments will include visual acuity testing, slit lamp examination of the anterior eye segment, intraocular pressure, and fundoscopy. Additional examinations such as specular microscopy (that enables a magnified, direct view of the corneal epithelium), corneal pachymetry, retinal optical coherence tomography (OCT), and dilated fundoscopy will be performed as clinically indicated.

9. STATISTICAL PLAN:

The primary objective is to evaluate the safety and tolerability of infigratinib as neoadjuvant therapy. Up to 20 patients will be enrolled in the study. The study will estimate proportion of patients who are not able to complete treatment (discontinuation) due to excessive toxicity along with the 90% exact confidence interval (NOTE: excessive toxicity is defined as treatment related adverse events that cause patients not to complete 2-cycles of planned treatment schedule). Toxicities will be tabulated using frequency and percentage by grade and their relations to treatment. Assuming a 30% of discontinuation due to excessive toxicity, the 90% confidence interval would be (13.1%, 46.9%) with a sample size of 20. Toxicity data will be summarized for the whole group of patients and for patients with eGFR \geq 50 and eGFR 30-49 separately. The safety analysis included all patients who received at least one dose of infigratinib.

Toxicity monitoring:

The study will monitor the incidence of not completing treatment or delay >14 days of surgery due to excessive toxicity using this monitoring rule. That is stop the trial early if $\text{Prob}(\text{Ptox} > 0.3 | \text{data}) > 0.85$. Where Ptox denotes the proportion of patients not being able to complete treatment or delay >14 days of surgery. The corresponding stopping boundaries are that the trial will be stopped early if at any time it is observed that $(n \text{ of patients not completing treatment or delay } >14 \text{ days of surgery due to excessive toxicity} / N \text{ of patients treated}) \geq 3/5, 4/(6-8), 5/(9-10), 6/(11-13), 7/(14-16), \text{ and } 8/(17-19)$. This stopping rule will be applied for each cohort of eGFR \geq 50 and eGFR 30-49 separately. If one cohort stops early due to excessive toxicity, the other will continue accruing as per protocol criteria and toxicity monitoring rule.

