The following table displays the operating characteristics for safety monitoring, assuming prior distribution for Ptox is beta(0.3, 0.7) and for a maximum sample size of 20. Since we do not have information for proportions of eGFR \geq 50 and eGFR 30-49, it would not be feasible to assess OCs for each cohort.

OCs for toxicity monitoring using a maximum sample size of 20

Rate of discontinued treatment due to toxicity/intolerance	Probability of early stop	Avg. N of patients treated
0.1	0.012	19.8
0.2	0.10	18.7
0.3	0.341	16.0
0.4	0.655	12.4
0.5	0.886	9.0

The secondary efficacy endpoint is objective response after 2 cycle treatment of infigratinib. We will estimate the objective response rate along with the 90% confidence interval. Fisher's exact test will be used to explore the difference in response between the two cohorts of patients.

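### The toxicity stopping rule defines its event inconsistently: a drug-caused surgery delay after two completed cycles is left out of the boundary count but included in Ptox

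*Combined protocol and SAP*

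**What the plan says.** Section 2.7 sets the endpoint: "The primary endpoint is the proportion of patients who are not able to complete treatment due to excessive toxicity". A note in the first paragraph of Section 9 explains the key term: "excessive toxicity is defined as treatment related adverse events that cause patients not to complete 2-cycles of planned treatment schedule".

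The toxicity monitoring paragraph of Section 9 then describes the monitored event three times:

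- **Monitoring sentence:** "The study will monitor the incidence of not completing treatment or delay >14 days of surgery due to excessive toxicity using this monitoring rule".
- **Ptox sentence**, defining the quantity in the posterior criterion (stop if the probability that Ptox exceeds 0.3 is above 0.85): Ptox "denotes the proportion of patients not being able to complete treatment or delay >14 days of surgery". No cause is named.
- **Boundary sentence**, giving the counts staff will tally: its numerator again ties the event to excessive toxicity.

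The operating-characteristics table that follows is computed "assuming prior distribution for Ptox is beta(0.3, 0.7) and for a maximum sample size of 20". Its rate column is labelled as treatment discontinued for toxicity or intolerance, with no mention of surgery delay.

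On timing, Section 5.1 says: "Surgery will be performed during weeks 8-9 (week 8 being the off-week of 2nd cycle". Each cycle is 28 days, three weeks on and one week off.

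**The concern.** The trial gives drug before surgery to patients with localized or locally advanced disease, so toxicity that postpones the operation is a harm in its own right. The delay limb is the only part of the numerical stopping rule that addresses it. Naming it separately suggests that it was meant to add patients whom the non-completion limb misses.

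The note's definition undoes that. Consider a patient who takes both cycles as planned and whose surgery is then held back more than 14 days by a drug-related adverse event. The boundary numerator leaves this patient out and Ptox counts them. Two people applying Section 9 in good faith could reach different counts, and the count decides whether a cohort stops.

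**Working it through.** **1. Substituting the definition.** Let E be excessive toxicity, C̄ non-completion of two cycles, and D a surgery delay of more than 14 days. By the note, E implies C̄. A delay due to E therefore lies inside non-completion due to E, and (C̄ due to E) or (D due to E) reduces to C̄ due to E. The delay limb adds zero patients. It makes no difference whether the phrase about excessive toxicity qualifies both limbs or only the delay, because the delay is qualified either way.

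**2. One patient under each wording.** Take the patient who completes both cycles and then has a drug-related delay of more than 14 days.

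| Place in Section 9 | Counted? |
|---|---|
| Primary endpoint (note) | No |
| Monitoring sentence | No |
| Ptox sentence | Yes |
| Boundary numerator | No |
| Operating-characteristics label | No (delay not mentioned) |

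A completer delayed for a scheduling reason would also count under the Ptox sentence, since it names no cause.

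**3. Reproducing the plan's figures.** Inputs are the beta(0.3, 0.7) prior, threshold 0.3, cut-off 0.85 and maximum N of 20, all from Section 9. The boundary at n is the smallest r with 1 − BetaCDF(0.3; 0.3 + r, 0.7 + n − r) > 0.85. For example, at n = 5 the probability is 0.637 for r = 2 and 0.894 for r = 3, so the boundary is 3. All printed boundaries for n = 5 to 19 match. An exact binomial recursion applying them after each patient gives:

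| True rate | P(stop), printed | P(stop), recomputed | Average N, printed | Average N, recomputed |
|---|---|---|---|---|
| 0.1 | 0.012 | 0.0116 | 19.8 | 19.84 |
| 0.2 | 0.10 | 0.103 | 18.7 | 18.70 |
| 0.3 | 0.341 | 0.3405 | 16.0 | 16.04 |
| 0.4 | 0.655 | 0.655 | 12.4 | 12.39 |
| 0.5 | 0.886 | 0.8857 | 9.0 | 9.04 |

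The table is arithmetically right. It depends only on the event rate, so it holds under any definition of the event.

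**4. What the choice of definition does.** Let d be the non-completion rate due to drug toxicity and s the share of completers with a drug-caused delay of more than 14 days. Literally, the counted rate is d. With a working delay limb it is d + (1 − d)s. The documents give no value for s, so the values below are assumptions. The same recursion, for one group of 20, gives:

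| d | s | Composite rate | P(stop), literal | P(stop), delays counted |
|---|---|---|---|---|
| 0.10 | 0.05 | 0.10 + 0.90 × 0.05 = 0.145 | 0.012 | 0.037 |
| 0.10 | 0.10 | 0.10 + 0.90 × 0.10 = 0.19 | 0.012 | 0.088 |
| 0.20 | 0.10 | 0.20 + 0.80 × 0.10 = 0.28 | 0.103 | 0.282 |
| 0.20 | 0.20 | 0.20 + 0.80 × 0.20 = 0.36 | 0.103 | 0.531 |

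**5. Smaller cohorts.** The rule applies separately to each eGFR cohort, and the plan gives no split. For an assumed cohort of 10, rates of 0.20 and 0.28 give stopping probabilities of 0.087 and 0.217.

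**6. Timing.** The last planned dose is on day 28 + 21 = 49, and cycle 2 ends on day 2 × 28 = 56. Section 9 does not say which of these marks completion. It also gives no date from which the 14 days of delay are counted; Section 5.1 offers a window rather than a day.

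**The case against.** The strongest reply is that the intent is plain. Nobody adds a separately named delay limb in order to count nobody, the note sits in the primary-endpoint paragraph, and Ptox, the quantity in the formal criterion, is defined so that a delayed completer counts. On that view a sensible team would count the delay anyway. This stands in part: a reader might infer that the delay limb can never add a patient, and the Ptox sentence rules that out. But the boundary numerator is the working instruction, and it carries the restrictive phrase. Nor does the Ptox wording express the evident intent, because it would also count delays unrelated to the drug.

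A reader might also infer that severe or fatal drug toxicity after the last dose never counts. The documents do not support that. Days 50 to 56 fall inside cycle 2, so an event then could be read as non-completion. Later events may miss the primary endpoint and the numerical boundary, but they are not unmonitored. Serious events are reported to 30 days after the last dose, and later if related (Section 8.2.1.4). Adverse events and deaths within 30 days are summarized (Section 9.1.1.1). Toxicity summaries go to the IND Office for review (Section 9.1.1.3), and the study may be terminated for drug safety concerns (Section 6.2). These are descriptive or discretionary and do not feed the boundary, but they exist. Bringing late Grade 4 events that do not delay surgery into the count would be a preference, not a correction.

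Finally, the effect may be small. Section 2.4.2 reports 10.1% discontinuing for related adverse events in the phase 1 study, which was a different population. At a 10% base rate the differences in the working are modest.

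**Conclusion.** The point holds as an inconsistency. Section 9 has no single definition of the event its stopping rule counts. Under the boundary wording the delay limb contributes no patients, under the Ptox wording it contributes delays from any cause, and the table label omits it. It should be corrected before the rule is applied, because the wording can decide whether a boundary is reached.

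The size is illustrative only. It runs from 0.012 against 0.037 (10% non-completion, 5% of completers delayed) to 0.103 against 0.531 (20% and 20%). It rests on assumed delay rates, independent patients with a constant rate, and one group of 20 although the rule is applied per eGFR cohort. The boundaries and the operating-characteristics figures themselves are correct.

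**What to change.** Keep the note's definition for the primary endpoint. In the toxicity monitoring paragraph, use one event in the monitoring, Ptox and boundary sentences and in the operating-characteristics label: a treatment-related adverse event that causes either non-completion of two cycles or a surgery delay of more than 14 days, whether or not both cycles were completed.

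Also state:

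- the reference date from which the delay is measured;
- whether completion means the last planned dose or the end of the 28-day second cycle;
- whether surgery never performed because of a treatment-related adverse event, including death, falls under the delay limb;
- how the report in Section 9.1.1.3, triggered once the first five evaluable patients per cohort complete two cycles, handles patients whose delay status is not yet known.

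Report how many patients enter the count through each limb.

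The cost is a few sentences and one column label. Boundaries, prior and table figures do not change. The downside is that a few more patients may count towards stopping.

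### The planning interval for the primary endpoint, (13.1%, 46.9%), is a normal approximation, although the plan specifies an exact 90% interval; the exact one for 6/20 is (14.0%, 50.8%)

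*Combined protocol and SAP*

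**What the plan says.** Section 2.7 defines the endpoint as a single binary proportion: "The primary endpoint is the proportion of patients who are not able to complete treatment due to excessive toxicity".

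Section 9 (Statistical Plan) sets the size, "Up to 20 patients will be enrolled in the study", and the method of estimation. The study will estimate the proportion of patients "not able to complete treatment (discontinuation) due to excessive toxicity along with the 90% exact confidence interval".

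Later in the same paragraph comes the precision statement: "Assuming a 30% of discontinuation due to excessive toxicity, the 90% confidence interval would be (13.1%, 46.9%) with a sample size of 20". That sentence names no method. No other section gives a different interval method for this endpoint or says that a normal approximation is used for planning.

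**The concern.** The printed interval is symmetric about 30%, at 16.9 points either side. An exact binomial interval for 6 events in 20 is not symmetric, so the figure could not have come from the method the plan names.

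This is the only precision figure given for the primary endpoint; the table of operating characteristics in Section 9 concerns early stopping. A reader will take 46.9% as the upper limit the specified analysis would return if 6 of 20 patients discontinued. If that result occurs, the reported interval will differ from the plan's own illustration, and someone will ask whether the method was changed. The printed figure is also too favourable at the upper limit, which is the limit I would look at first for a toxicity rate.

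**Working it through.** **Inputs (all from Section 9).** n = 20; assumed proportion 0.30, so x = 0.30 × 20 = 6 exactly, with no rounding of the event count; two-sided 90% confidence, so 5% in each tail for equal-tailed limits and z = 1.645.

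**Step 1. Reproduce the printed figure.** Wald interval:

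p ± z × √(p(1 − p)/n) = 0.30 ± 1.645 × √(0.30 × 0.70 / 20) = 0.30 ± 1.645 × 0.1025 = 0.30 ± 0.1685

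This gives (0.1315, 0.4685). To four decimals in per cent it is (13.145%, 46.855%), which rounds to the printed (13.1%, 46.9%) at both ends.

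**Step 2. Compute the interval the plan specifies.** Clopper-Pearson limits are beta quantiles:

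- Lower: 5th percentile of Beta(x, n − x + 1) = Beta(6, 15) = 0.1396
- Upper: 95th percentile of Beta(x + 1, n − x) = Beta(7, 14) = 0.5078

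Check: P(X ≥ 6 | p = 0.1396) = 0.050 and P(X ≤ 6 | p = 0.5078) = 0.050. The exact interval is therefore (14.0%, 50.8%).

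**Step 3. Does the choice of exact method matter?** The plan does not name one, so the alternatives were computed, together with common non-exact intervals, all at 90% for 6/20.

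| Method | Lower | Upper |
|---|---|---|
| Printed in Section 9 | 13.1% | 46.9% |
| Wald | 13.1% | 46.9% |
| Exact, Clopper-Pearson | 14.0% | 50.8% |
| Exact, inverting the two-sided binomial test | 14.7% | 50.0% |
| Exact, Blaker | 14.1% | 50.0% |
| Mid-p | 15.4% | 48.7% |
| Wilson | 16.4% | 48.4% |
| Agresti-Coull | 16.2% | 48.5% |
| Jeffreys | 15.8% | 48.2% |
| Wald with continuity correction | 10.6% | 49.4% |
| t-based | 12.3% | 47.7% |
| Credible interval, beta(0.3, 0.7) prior | 15.1% | 47.1% |

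Only Wald matches. Every exact upper limit is at least 50.0%.

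**Step 4. Size of the difference, Clopper-Pearson against printed** (from unrounded limits).

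- Upper limit: 0.5078 − 0.4685 = 0.0393, or 3.9 points higher
- Lower limit: 0.1396 − 0.1315 = 0.0081, or 0.8 points higher
- Width: 0.3683 − 0.3371 = 0.0312, or 3.1 points wider (36.8 against 33.7)
- Shape: the exact interval runs 16.0 points below 30% and 20.8 above it

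**Step 5. What the printed upper limit means in probability.** At a true rate of 46.9%, P(X ≤ 6 | n = 20) = 0.097. An equal-tailed exact 90% limit (Clopper-Pearson) holds this tail at 0.05.

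**Step 6. Coverage at the plan's own assumption.** With a true rate of 30% and n = 20, the Wald interval contains 30% when x is 4 to 9, which has probability 84.5%. The Clopper-Pearson interval contains it when x is 3 to 9, probability 91.7%. The nominal level is 90%.

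**The case against.** The best defence is that the planning sentence never calls its interval exact. The word is attached to the interval the study will report; the illustration says only that it is a 90% interval. Read that way, the plan shows a correctly computed normal approximation for orientation and will analyse the data exactly, so the fault is a missing label. This does not rescue the figure. Exact is the only method named for this endpoint, the two statements share a paragraph and a confidence level, and nothing tells the reader that the method has changed.

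The second objection is that little follows from the error, and this stands. The limit of 20 patients is not derived from a target width. Early stopping rests on a separate posterior-probability rule with a beta(0.3, 0.7) prior. No decision in the plan is tied to either confidence limit. The final report will use the exact interval for whatever count is observed. With either interval, the message is that 20 patients give wide limits.

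A narrower point also stands. The 5% tail benchmark in Step 5 applies only to equal-tailed limits. At the 50.0% upper limit given by test inversion and by Blaker's method, P(X ≤ 6) is 5.8%, so those valid exact intervals do not meet it either. The comparison should be read as one with Clopper-Pearson.

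**Conclusion.** The point holds. The precision stated for the primary endpoint was not obtained by the method specified for that endpoint. Against Clopper-Pearson it understates the upper limit by 3.9 points and the width by 3.1 points; the lower limit is also 0.8 points too low. One practical reading changes: the printed interval suggests that 6/20 would exclude a 50% discontinuation rate, and the Clopper-Pearson interval does not exclude it.

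The size of the differences assumes that exact means Clopper-Pearson, the usual reading. The conclusion that the figure is not exact does not need that assumption, because none of the three exact methods gives 46.9%. The consequence is limited to the stated figure, which should be corrected; the design is sound on this point.

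**What to change.** In Section 9, replace (13.1%, 46.9%) with (14.0%, 50.8%) and describe it as the exact (Clopper-Pearson) 90% confidence interval for 6 of 20 patients. Naming the method also settles which exact interval the final analysis will use, which the plan leaves open. If the sponsor means a different exact method, it should name that one and print its interval.

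Labelling the present figure as a normal approximation would remove the contradiction, but the plan would still show a precision that its own analysis would not return.

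The cost is one figure and one label. The stated precision becomes slightly less favourable. The sample size, stopping rule and analysis method need no change.

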9.1.1.3 Safety and Efficacy Monitoring

The Investigator is responsible for completing a toxicity/efficacy summary report, and submitting it to the IND Office Medical Affairs and Safety Group, for review and approval. This should be submitted after the first 5 evaluable patients per cohort, complete 2 cycles of study treatment, and every 2-3 evaluable patients per cohort, thereafter, as illustrated by the stopping boundaries in section 10.

A copy of the cohort summary should be placed in the Investigator's Regulatory Binder under "sponsor correspondence".

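### The stopping counts start at 3/5, although three events in a cohort's first 3 or 4 patients already settle that stop: write the first boundary as 3/(3-5)

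*Combined protocol and SAP*

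**What the plan says.** Section 9 (Toxicity monitoring) states the rule in two forms. The first is a probability rule: stop if the posterior probability that Ptox exceeds 0.3 is above 0.85. It carries no minimum number of patients. The second is a list of counts, introduced by "the trial will be stopped early if at any time it is observed that" the ratio of events to patients treated reaches 3/5, 4/(6-8), 5/(9-10), 6/(11-13), 7/(14-16) or 8/(17-19). Nothing is listed for 1 to 4 patients, and no reason is given for starting at 5.

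The event is failure to complete treatment, or a surgery delay of more than 14 days, due to excessive toxicity. The operating characteristics are computed "assuming prior distribution for Ptox is beta(0.3, 0.7) and for a maximum sample size of 20". On scope, "Up to 20 patients will be enrolled in the study", and "This stopping rule will be applied for each cohort of eGFR" ≥50 and eGFR 30-49 separately. The sizes of the two cohorts are not known in advance ("Since we do not have information for proportions of eGFR" ≥50 and eGFR 30-49).

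On reporting, Section 9.1.1.3 says of the toxicity/efficacy summary: "This should be submitted after the first 5 evaluable patients per cohort, complete 2 cycles of study treatment". Further reports follow every 2-3 evaluable patients per cohort.

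**The concern.** A boundary of 3/5 is decided as soon as the third event occurs, even if only 3 or 4 patients have been treated. Whatever happens to the remaining patients, the count at n=5 will be at least 3. Yet neither the list of counts nor the reporting schedule calls for action before the fifth patient. Followed as written, they allow one or two more patients to begin a drug that the cohort is already bound to stop.

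The two forms of the rule also disagree below n=5. The probability rule is already met at 3/3 and 3/4, where the list is silent. It is met as well at 1/1, 2/2 and 2/3, where the list is also silent. A reader cannot tell from Section 9 which form governs the first four patients of a cohort.

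**Working it through.** **Inputs, all from Section 9.** Prior beta(0.3, 0.7); cutoff P(Ptox > 0.3 | data) > 0.85; the listed counts for n = 5 to 19; maximum N = 20.

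**Step 1: reproduce the plan's figures.** After x events in n patients the posterior is beta(0.3 + x, 0.7 + n − x). The smallest x with posterior probability above 0.85 matches the listed count at every n from 5 to 19. For example, 3/5 gives 0.894 and 2/5 gives 0.637. An exact recursion over one stream of 20, checked after every patient from n = 5 to n = 19, gives:

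| True rate | P(early stop), plan | P(early stop), recomputed | Mean N, plan | Mean N, recomputed |
|---|---|---|---|---|
| 0.1 | 0.012 | 0.0116 | 19.8 | 19.84 |
| 0.2 | 0.10 | 0.103 | 18.7 | 18.70 |
| 0.3 | 0.341 | 0.3405 | 16.0 | 16.04 |
| 0.4 | 0.655 | 0.655 | 12.4 | 12.39 |
| 0.5 | 0.886 | 0.8857 | 9.0 | 9.04 |

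The plan's table therefore describes the listed counts, starting at n = 5.

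**Step 2: the posterior below n = 5.**

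| Events/patients | Posterior | Above 0.85? | Is 3/5 already certain? |
|---|---|---|---|
| 1/1 | 0.854 | yes | no |
| 2/2 | 0.961 | yes | no |
| 2/3 | 0.869 | yes | no |
| 3/3 | 0.989 | yes | yes |
| 3/4 | 0.953 | yes | yes |
| 4/4 | 0.997 | yes | yes |

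Applying the bare probability rule from n = 1 gives a stopping probability of 0.497 and a mean N of 12.0 at a true rate of 0.3. The table states 0.341 and 16.0, so the bare rule is not the one that was evaluated.

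**Step 3: how often the gap arises.** The chance that the third event falls within the first 4 patients is p³ + 3p³(1 − p):

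- p = 0.3: 0.027 + 0.0567 = 0.084
- p = 0.4: 0.064 + 0.1152 = 0.179
- p = 0.5: 0.125 + 0.1875 = 0.3125

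**Step 4: what stopping at once saves.** A stop at 3/3 spares 2 patients relative to n = 5, and a stop at 3/4 spares 1. The mean saving is 2p³ + 3p³(1 − p):

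- p = 0.3: 0.054 + 0.0567 = 0.11
- p = 0.4: 0.128 + 0.1152 = 0.24
- p = 0.5: 0.25 + 0.1875 = 0.44

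The recursion with 3/3 and 3/4 added agrees. Mean N goes from 16.04 to 15.93, 12.39 to 12.15, and 9.04 to 8.60. At rates 0.1 and 0.2 it goes from 19.84 to 19.83 and from 18.70 to 18.67. The probability of early stop is identical at all five rates, because every added stop would have occurred at n = 5 anyway.

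**Step 5: a cohort that ends at 3 or 4 patients.** No n = 5 look exists there, so 3/(3-4) is a new boundary. In a cohort of 4 at a true rate of 30% it is met with probability 0.084, against 0 under the listed counts. It spares at most one patient (a stop at 3/3).

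**The case against.** A formal count-based look from 5 patients onward is an ordinary design choice, and the gain from moving it is slight. That stands: the mean saving is under half a patient at every rate in the plan's table. The calculation also assumes that each outcome is known before the next patient starts. The event takes up to two 28-day cycles plus a surgery window to observe, and the plan specifies no accrual pause. Patients 4 and 5 may already be on drug when the third event is recognised. Because the denominator is patients treated, 3/5 would then already be met. The savings above are upper limits.

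A reader might infer that a cohort of 4 or fewer can never be stopped. The documents do not support this. The list has no count for such a cohort, but the probability rule in the same paragraph has no minimum n and would stop at 3/3, 3/4 or 4/4. Section 6.2 also allows premature termination at any time for drug safety concerns, and Section 8.2.1.4 has its own reporting timelines for serious events. The defect is that rule and list disagree.

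Nor is the change free of any trade-off. It is pure curtailment only where the cohort would reach 5 patients. In a smaller cohort it introduces a stop that the listed counts do not contain.

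**Conclusion.** The point holds as a minor one. The listed counts and the reporting schedule let one or two more patients start in a cohort whose stop is already determined, in states where the plan's own criterion is met more strongly than at 3/5. Stopping at the third event leaves the stopping probabilities unchanged for any cohort that reaches 5 patients. In a single stream of 20 it lowers mean N by 0.11 to 0.44 at true rates of 30% to 50%, and by no more than 2 patients on any path.

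These figures assume independent events at a constant rate, outcomes known before the next enrolment, and a look after every patient from the first boundary onward. Cohort-level figures depend on the eGFR split, which the plan says is unknown. The conflict between the probability rule and the counts below n = 5 does not depend on these assumptions and should be resolved in any case.

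**What to change.** Make three edits:

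1. In Section 9, write the first boundary as 3/(3-5) and leave the later counts as they are.
2. In Section 9.1.1.3, have a third event in a cohort trigger the summary report at once if it comes before 5 evaluable patients.
3. In Section 9, state that the counts, not the bare probability rule, govern below n = 5. Otherwise the rule would also stop at 1/1, 2/2 and 2/3, which does not match the operating-characteristics table.

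The cost is one term, one clause and one sentence. The stopping probabilities in the table stay as they are. Mean N at rates 0.3, 0.4 and 0.5 becomes 15.9, 12.2 and 8.6. The one statistical cost is the new boundary in a cohort that ends at 3 or 4 patients, and the sponsor should accept it knowingly.
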